8.2. ADVERSE EVENT (AE) MONITORING

Following study informed consent form signature, at each visit, after the patient has had the opportunity to spontaneously mention any problems, the Investigator or appropriate designee should inquire about AEs by asking the standard questions:

- “Have you had any health problems since your last study visit?”
- “Have there been any changes in the medicines you take since your last study visit?”

AEs should be reported for any clinically relevant change in concomitant condition(s) that is the result of an untoward (unfavorable and unintended) change in patient's medical conditions. Changes in any protocol-specific ocular or systemic parameter evaluated during the study are to be reviewed by the Investigator. In addition, the patient's responses to any questionnaire utilized during the study are to be reviewed by the Investigator. Any untoward (unfavorable and unintended) change in a protocol-specific parameter or questionnaire response that is clinically relevant is to be reported as an AE. These clinically relevant changes will be reported regardless of causality.

All AEs should be followed-up to determine outcome of the reaction.

In order to collect as complete as possible information in the clinical study database, all ADRs and SAEs ongoing at the time the subject's study participation ends should be evaluated within 10 days after the final visit. After this period, all unresolved ADRs and SAEs will be reported as “ongoing” in the eCRF.

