8.3. RECORDING

AE data should be obtained through observation of the patient, from any information volunteered by the patient, and through patient questioning.

Adverse Events:

All AEs (non-serious and serious) that occur during the course of the study will be recorded in the eCRF. Any pre-existing medical conditions or signs/symptoms present in a patient prior to the start of the study (i.e., before informed consent is signed) should be specified in the dedicated eCRF sections. Subsequent to signing an informed consent form, all untoward medical occurrences that occur during the course of the study must be documented on eCRF. AEs will be collected till last Follow Up visit (week 24).

When possible, signs and symptoms indicating a common underlying pathology should be documented as one comprehensive event. For each recorded event, the AE documentation must include the onset date, outcome, resolution date (if event is resolved), intensity (i.e., severity), any action with study treatment taken as a result of the event, and an assessment of the adverse event relationship to the study treatment.

Serious Adverse Events:

The Investigator must record all SAEs, including sight-threatening events, occurring at any time during the study (after signature of the informed consent) regardless of presumed causal relationship, on the Serious Adverse Event form in the eCRF of the EDC system within 24 hours of learning of the event; information on the SAE must also be recorded on a specific Non-Carbon Repeat SAE form (included in the Investigator's Site File).

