8.3.2. Severity of AEs

The Investigator will grade the severity of any AE using the definitions in the Table below. For each episode, the highest severity grade attained should be reported.

Severity of the Adverse Event

Mild	Grade 1 - Does not interfere with patient's usual function (awareness of symptoms or signs, but easily tolerated [acceptable]).
Moderate	Grade 2 - Interferes to some extent with patient's usual function (enough discomfort to interfere with usual activity [disturbing]).
Severe	Grade 3 - Interferes significantly with patient's usual function (incapacity to work or to do usual activities [unacceptable])

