9.4.5. Analysis of safety variables

Adverse events (AEs) will be coded by System Organ Class (SOC) and Preferred Term (PT), using the Medical Dictionary for Regulatory Activities (MedDRA).

Treatment-emergent AEs (TEAEs) are all events occurring or worsening after the first dose of the IMP. TEAEs will be presented by treatment arm in terms of number of AEs and their incidence by System Organ Class (SOC) and Preferred Terms (PT) using MedDRA. Analyses will be provided also by seriousness, relationship to treatment, severity and study period (treatment or follow-up).

Individual AEs will be listed in patient data listings.

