11.1 Adverse events

Adverse Events (AEs) started before administration of study treatment will be considered as pre-treatment; any AE started on or after the date of the first dose of study medication or started prior to first dose and worsened in severity after the first dose will be considered as Treatment-Emergent Adverse Event (TEAE).

In case of missing or incomplete dates not allowing a direct allocation to any of the two categories of AEs (pre-treatment/TEAE), an allocation will be done according to the available parts of the onset and the end dates (see Table 6). In case of TEAE, the event can be further classified as:

- On Treatment period, or
- On Follow-up period

according to the available parts of the onset and the end dates (see Table 6).

All AEs will be coded by SOC and PT according to MedDRA thesaurus. In addition, each AE will be graded to capture the relationship to IMP and severity (see protocol for details).

Pre-treatment AEs will be presented in the listings only.

TEAE summaries will be presented, displaying frequencies and percentages of patients reporting AEs within each SOC in decreasing order of total frequency. Along with AEs, number of events will be reported. On each of these summaries, patients will be counted only once per SOC and, within each SOC, patients will be counted only once per PT.

“Possible”, “Probable” and “Highly Probable” or missing relationships will be considered as related to study drug (ADR – Adverse Drug Reaction) for the summary tables. “None” and “unlikely” relationships will be considered not related to study drug.

The following table will be presented by treatment group and overall:

- A summary overview (patient with at least one event, percentage, and number of events) of:
 - TEAEs,
 - Ophthalmic TEAEs,
 - Non-Ophthalmic TEAEs,
 - severe TEAEs,
 - severe Ophthalmic TEAEs,
 - severe Non-Ophthalmic TEAEs,
 - serious TEAEs,
 - serious Ophthalmic TEAEs,
 - serious Non-Ophthalmic TEAEs,
 - non-serious TEAEs,
 - ADRs,
 - Ophthalmic ADRs,
 - Non-Ophthalmic ADRs,
 - serious ADRs,
 - TEAEs leading to discontinuation of IMP,
 - TEAEs leading to discontinuation of study,
 - TEAEs leading to death.

The following tables will be presented by treatment group:

- Summary of Ophthalmic TEAEs by primary SOC and PT and by study period (on treatment/follow-up and overall).
- Summary of Non-Ophthalmic TEAEs by primary SOC and PT and by study period (on treatment/follow-up and overall).

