12.5 Partial date conventions

Table 6: Algorithm for Treatment Emergence of Adverse Events

AE START DATE	AE STOP DATE	RULE for TEAE definition	RULE for “Treatment”/“Follow-up” study period definition for TEAE summaries
Known	Known, Partial or Missing	If AE start date < IMP start date, then not TEAE If AE start date \geq IMP start date, then TEAE	In case of Treatment Discontinuation: If start date \geq Date of last IMP intake, then Follow-up study period for TEAE occurrence. Otherwise, Treatment study period for TEAE occurrence. In case of NO Treatment Discontinuation: If start date \geq Date of “Day 21” visit, then Follow-up study period for TEAE occurrence. Otherwise, Treatment study period for TEAE occurrence.
Partial, but known components show that it cannot be on or after IMP start date	Known, Partial or Missing	Not TEAE	Not applicable

AE START DATE	AE STOP DATE	RULE for TEAE definition	RULE for "Treatment"/"Follow-up" study period definition for TEAE summaries
Partial, could be on or after IMP start date	Known	If AE stop date < IMP start date, then not TEAE If AE stop date \geq IMP start date, then TEAE	If TEAE, then Treatment study period for TEAE occurrence.
	Partial	Impute stop date as latest possible date (i.e. last day of month if day unknown or 31st December if day and month are unknown), then: If AE stop date < IMP start date, then not TEAE If AE stop date \geq IMP start date, then TEAE	
	Missing	Assumed TEAE	
Missing	Known	If AE stop date < IMP start date, then not TEAE If AE stop date \geq IMP start date, then TEAE	If TEAE, then Treatment study period for TEAE occurrence.
	Partial	Impute AE stop date as latest possible date (i.e. last day of month if day unknown or 31st December if day and month are unknown), then: If AE stop date < IMP start date, then not TEAE If AE stop date \geq IMP start date, then TEAE	
	Missing	Assumed TEAE	

NOTE: Assignment to "Treatment" or "Follow-up" study period is applicable only for TEAEs.

Table 7: Algorithm for Prior/Concomitant medications

MEDICATION START DATE	MEDICATION STOP DATE	RULE for prior or concomitant categorization
Known	Known	
If medication stop date < date of first dose of IMP, assign as prior
 
If medication stop date \geq date of first dose of IMP, assign as concomitant

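### Two rows of SAP Table 6 omit the worsening criterion for treatment-emergent AEs, and the required AE fields do not by themselves show worsening after first dose

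*SAP*

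**What the plan says.** Three places define or apply treatment emergence.

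- Protocol 9.4.5: "Treatment-emergent AEs (TEAEs) are all events occurring or worsening after the first dose of the IMP".
- SAP 11.1 includes an AE that "started prior to first dose and worsened in severity after the first dose will be considered as Treatment-Emergent Adverse Event (TEAE").
- SAP 12.5, Table 6, row for a known start date: "If AE start date < IMP start date, then not TEAE". The next row, for a partial start date whose known parts place it before the first dose, is an unconditional non-TEAE.

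SAP 11.1 introduces Table 6 with a limit on its scope: "In case of missing or incomplete dates not allowing a direct allocation to any of the two categories of AEs". It also sends TEAEs to Table 6 for assignment to the treatment or follow-up period. On output, SAP 11.1 says "Pre-treatment AEs will be presented in the listings only".

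On recording, Protocol 8.3 requires that "the AE documentation must include the onset date, outcome, resolution date (if event is resolved), intensity (i.e., severity"), together with action taken and relationship to treatment. Protocol 8.3.2 adds: "For each episode, the highest severity grade attained should be reported". AE recording starts at informed consent (Protocol 8.3), and the wash-out between screening and baseline lasts 8 to 10 days (Protocol 6.1).

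**The concern.** The definition and the algorithm disagree on one kind of event: an AE that begins in the wash-out and becomes more severe after dosing starts. A programmer who follows the table will class it as pre-treatment, and it will then be absent from every TEAE and ADR summary.

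The incidence and frequency of TEAEs is the safety endpoint in Protocol 7.1.4 and SAP 3.2.4 (the synopsis also names AEs in general). Patients stop other ophthalmic treatment at screening, so ocular AEs that begin before the first dose are plausible. Worsening of such an event on a topical eye drop bears on tolerability. If worsening were more frequent on cenegermin than on vehicle, leaving these events out would make the comparison look more favourable to cenegermin. The documents give no evidence either way on that condition.

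There is also a question about the data. Even if SAP 11.1 is followed, the program must know whether severity rose after the first dose, and the fields that the protocol lists do not say so.

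**Working it through.** The plan gives no figure for this point, so there is nothing to reproduce. The check applies both rules to the same AE histories and then asks whether the required record can tell the histories apart.

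**Rules**

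- Table 6, known start: TEAE if start date ≥ first IMP date; otherwise not.
- SAP 11.1: TEAE if start date ≥ first IMP date, or if the start is earlier and severity rises after first dose.

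**Illustrative histories** (start day counted from first dose = 0)

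| History | Start | Grade before dose | Highest grade after dose | Table 6 | SAP 11.1 |
|---|---|---|---|---|---|
| a. Starts before dose, no worsening | -4 | 1 | 1 | not TEAE | not TEAE |
| b. Starts before dose, worsens after | -4 | 1 | 3 | not TEAE | **TEAE** |
| c. Starts on the day of first dose | 0 | none | 2 | TEAE | TEAE |
| d. Starts after dose, then worsens | +5 | none | 3 | TEAE | TEAE |

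The rules agree in three of four histories. Only (b) differs. With a worsening branch in Table 6 they agree in all four.

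**Can the record identify (b)?** The required fields hold one onset date and one intensity, which is the highest grade.

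- AE already at grade 3 before first dose: onset -4, grade 3.
- AE at grade 1 before first dose and grade 3 afterwards: onset -4, grade 3.

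The two records agree in onset and grade, so SAP 11.1 cannot be applied from these fields alone. It needs the severity at first dose, a date of worsening, or a separate AE record.

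**Study period.** Table 6 assigns the treatment or follow-up period by start date. Suppose (b) is accepted as a TEAE under SAP 11.1, but the worsening came after the last dose. Its pre-dose start date would still place it in the treatment period.

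**Who is affected.** Only AEs that start after consent and before first dose, persist, and then worsen. Conditions present before consent go to other eCRF sections (Protocol 8.3). A clinically relevant change in them is reported as an AE in its own right (Protocol 8.2), so its onset falls on treatment.

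**The case against.** The best defence is that SAP 11.1 governs. It states the worsening criterion in full and calls on Table 6 for TEAE status only when dates are missing or incomplete. The table sits under a heading on partial dates. On that reading an AE with a known pre-dose start that worsened is allocated directly by SAP 11.1, and the known-date row serves only to assign the study period. A reader might infer from Table 6 that the plan has a settled rule removing all AEs that worsen on treatment from all safety reporting. The documents do not support that:

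- The protocol and SAP 11.1 both say the opposite of the table, so this is a contradiction and not a settled rule.
- AEs that start on or after first dose are TEAEs whether or not they worsen.
- The affected AEs stay in the listings. SAP 15.2 includes listings of all AEs, of AEs leading to IMP or study discontinuation, of SAEs and of ADRs, none titled as TEAE-only. SAP 8.3 tabulates discontinuations with reasons by arm regardless of TEAE status.
- Protocol 8.2 says "AEs should be reported for any clinically relevant change in concomitant condition(s") and extends this to clinically relevant changes in study parameters and questionnaire responses. A separate record at worsening is therefore not excluded. The eCRF and its completion guidelines were not available, and they may capture severity changes.

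These points narrow the concern but do not remove it. The known-date row states a TEAE rule for complete dates, and that row must be used because it holds the period rule for them. The partial-date row concerns incomplete dates, so the scope limit does not take it out of use, and it omits worsening too. Nothing in the documents tells sites to open a new record when a wash-out AE worsens. Protocol 8.3 also asks that signs and symptoms of a common pathology be recorded as one event where possible, which leans towards a single record.

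**Conclusion.** The contradiction is real. Two rows of Table 6 leave out a criterion that the protocol and SAP 11.1 both state, and the table misclassifies one kind of AE if it is programmed as written. The required AE fields do not by themselves let the criterion be applied; whether the eCRF does cannot be judged from the documents.

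The consequence is limited to AEs that begin in the 8 to 10 days before first dose and later worsen. It also depends on Table 6 prevailing over SAP 11.1 in the programming. The affected AEs would move from the summary tables to the listings; they would not vanish.

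No size can be given, because the documents report no wash-out AE rate and no worsening rate. It may be zero. For overall incidence, a patient with any other TEAE is still counted, so the loss there is smaller than the number of misclassified events. Counts by preferred term and severity could still change for such a patient. A bias towards cenegermin would require more worsening on drug than on vehicle, which nothing in the documents shows.

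**What to change.** 1. In both Table 6 rows for pre-dose starts, write: not TEAE unless severity worsened on or after first dose; if worsened, TEAE, with study period assigned by the date of worsening. This brings the table into line with SAP 11.1 and Protocol 9.4.5.
2. In the eCRF completion instructions or Protocol 8.3.2, ask that an AE ongoing at first dose that later worsens be entered as a new AE record with its own onset date and grade. Recording severity at first dose would serve equally well. If the eCRF already captures one of these, the SAP need only name the field.
3. Query AEs already recorded with a pre-dose onset and ongoing at first dose, so that any later worsening is dated before the blind data review (SAP 7.10) and the single database lock (SAP 7.9). This covers patients treated before the instruction is issued.

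The cost is a short change to the SAP, one site instruction and a few queries or extra AE records. The TEAE count may rise slightly.

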treatment, as pre-specified in the statistical analysis plan (SAP), the difference between both cenegermin dose regimens vs. placebo was statistically significant for both study groups (p=0.028 for cenegermin TID and p=0.007 for cenegermin BID [P-value versus Vehicle TID based on Fisher's exact test]). It is noteworthy that, while no clear dose ranging effect was observed on the tear function endpoints, symptoms recorded by the DE-specific and validated SANDE questionnaire showed a significant persistence of the beneficial effect of the higher dose-regimen (TID) over time and up to the full 16 weeks after the end of the 4 weeks treatment cycle. In fact, statistical significance vs. vehicle was reached at all follow-up timepoints for the TID with best result at week 12 (p=0.002 based on t-test; missing data imputed by LOCF). In addition, no difference was observed in the safety and tolerability profile of the experimental treatment. Specifically, up to 3 instillations per day of cenegermin ophthalmic solution in both eyes confirmed to be safe and well tolerated. The two cenegermin study groups have shown a similar tolerability. No serious adverse events were reported in the study. Adverse reactions were mild and transient, and occurred only during the 4-weeks treatment period of the 16-weeks cycle.

The results of these three randomized controlled studies in dry eye disease patients, as well as the results on reflex tear secretion obtained in the neurotrophic keratitis trials CCI [REDACTED] and CCI [REDACTED], suggests that cenegermin may be a safe and effective treatment option for patients with hyposecretive/aqueous tear-deficient dry eye disease. In all studies rhNGF was well tolerated and the reported ocular AEs were generally transient and mostly mild and moderate in intensity during the controlled treatment period and the follow-up period.

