4.2 Date of first and last administration of study drug

The date of first administration of study drug is defined as the date of first administration of IMP as per IMP Administration eCRF form (information transcribed from Patient Diary).

The date/time of last administration of study drug is defined as the Date of last treatment administration as per End of treatment eCRF form. This value has to be consistent with IMP Administration information recorded on the corresponding eCRF forms. In case of different dates, the latest will be used as treatment end.

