- Summary of TEAEs by primary SOC, PT and Severity.
- Summary of Serious TEAEs by Primary SOC and PT and by study period (on treatment/follow-up and overall).
- Summary of ADRs by Primary SOC and PT and by study period (on treatment/follow-up and overall).
- Summary of ADRs by Primary SOC and PT and Severity.
- Summary of TEAEs leading to IMP Discontinuation by Primary SOC and PT and by study period (on treatment/follow-up and overall).
- Summary of TEAEs leading to study Discontinuation by Primary SOC and PT and by study period (on treatment/follow-up and overall).
- Summary of TEAEs leading to Death by Primary SOC and PT.
- Listing of Deaths.

12. Derivations and date conventions

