12.1 Variable derivation

Table 3: Variable derivation rules

Parameter	Calculation
Screened	A patient is considered screened if (s)he has “Has written Informed Consent been obtained?” = Yes AND “Date of Informed Consent Signature at screening” filled
Screening failure	A patient is considered screening failure if (s)he has “Screen Failure date” filled
Enrolled	A patient is considered enrolled if (s)he has been screened and (s)he is not a screening failure.
Eligible eye	Assuming that all the inclusion/exclusion criteria are met: 
• If only one eye fulfills the criteria of Severe Sjögren's Dry Eye (“Which eye is diagnosed with Severe Sjögren's Dry Eye?” is answered with “Right Eye” or “Left Eye”) than the selected eye will be the “eligible eye”.• If both eyes fulfill the criteria of Severe Sjögren's Dry Eye (“Which eye is diagnosed with Severe Sjögren's Dry Eye?” is answered with “Both”) than the eligible eye will be selected according to the following rank:
i. the eye with lower Schirmer I score, otherwiseii. the eye with worse NEI score (cornea+conjunctival staining), otherwiseiii. the eye with worse investigator's judgement (“Were there any clinically significant abnormalities noted?” Equal to yes for a specific eye), otherwiseiv. the right eye.
Change from baseline	Each change from baseline will be defined as difference between the value at each post-baseline assessment and the baseline value.
Time since first diagnosis of Dry Eye	Randomization date - Date of diagnosis for eligible eye + 1

Parameter	Calculation
Time since first diagnosis of Severe Sjögren's Dry Eye	Randomization date - Date of diagnosis of Severe Sjögren's Dry Eye for eligible eye + 1
Total number of drops in the eligible eye taken during the treatment period	Sum of Morning/Afternoon/Evening Number of times the IMP has been administered for the eligible eye between Randomization visit date and End of Treatment date, considering 1 drop each time (morning, afternoon, evening). (from the eCRF form "IMP Administration" forms)
Total number of drops in the eligible eye scheduled during the treatment period	3*(Date of End of Treatment visit – Date of Randomization + 1) – (assessments not done on Randomization visit + assessments not done on End of Treatment visit)
The extent of exposure (days)	Date of last administration of IMP – Date of first administration of IMP + 1

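### For patients who stop treatment early, SAP Table 6 counts the last dosing day as follow-up, so a new event starting that day is tabulated in the wrong study period

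*SAP*

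**What the plan says.** SAP section 12.5, Table 6, has one column that decides whether an event is a TEAE and another that assigns each TEAE to the treatment or follow-up period. For a known start date in a patient who discontinues treatment, the period column compares the start date with the last intake date. If the start is on or after (≥) that date, the result is "Date of last IMP intake, then Follow-up study period for TEAE occurrence". All other starts fall to "Otherwise, Treatment study period for TEAE occurrence".

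Four other provisions bear on this rule:

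- SAP section 4.2 takes last administration from the "Date of last treatment administration as per End of treatment eCRF form"; if the eCRF forms disagree, the later date is used. The boundary is therefore a day on which drug was taken.
- SAP section 12.1, Table 3, computes exposure as "Date of last administration of IMP – Date of first administration of IMP + 1", which includes the last dosing day.
- SAP section 11.1 treats as treatment-emergent "any AE started on or after the date of the first dose of study medication", and also events that began before the first dose and worsened after it.
- For a partial or missing start date, Table 6 states: "If TEAE, then Treatment study period for TEAE occurrence".

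SAP section 11.1 uses the split in six summaries: ophthalmic TEAEs, non-ophthalmic TEAEs, serious TEAEs, ADRs, and TEAEs leading to discontinuation of IMP or of the study. One of them is specified as "Summary of TEAEs leading to IMP Discontinuation by Primary SOC and PT and by study period (on treatment/follow-up and overall").

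**The concern.** A typical tolerability stop runs as follows: the patient instils a drop, has a reaction that day, and takes no more drug. The event start date then equals the last dosing date, and the ≥ sign sends the event to follow-up. The table of TEAEs leading to IMP discontinuation would show it as arising after the treatment period, although it is the reason that treatment ended.

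The by-period tables are where a reader looks to separate reactions during dosing from later events. For patients who stop early, the rule removes from the treatment column the one day on which a reaction that causes an immediate stop would start.

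**Working it through.** No sample size, power or alpha figure enters this point, so there is no stated figure to reproduce. The check compares two date rules in the same SAP.

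**Inputs.** Let F be the date of first dose, L the date of last dose, and S the known start date of a new-onset event (S ≥ F).

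- Exposure days (SAP Table 3): L − F + 1.
- Period as written (SAP Table 6, discontinuation branch): follow-up if S ≥ L, otherwise treatment. The treatment-period days run from F to the day before L, which is L − F days.
- Period with a strict inequality: follow-up if S > L, otherwise treatment. The treatment-period days run from F to L, which is L − F + 1 days.

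As written, the rule gives (L − F + 1) − (L − F) = 1 day fewer than exposure for every patient who stops early. That day is always L.

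**Numbers, with F = Day 1:**

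| L | Exposure days | Treatment-period days as written | Treatment-period days with > |
|---|---|---|---|
| Day 1 | 1 | 0 | 1 |
| Day 2 | 2 | 1 | 2 |
| Day 10 | 10 | 9 | 10 |
| Day 14 | 14 | 13 | 14 |

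**Single events, with L = Day 10:**

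| S | As written | With > |
|---|---|---|
| Day 9 | Treatment | Treatment |
| Day 10 | Follow-up | Treatment |
| Day 11 | Follow-up | Follow-up |

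For a patient dosed only on Day 1, S ≥ 1 = L for every new-onset event with a known date, so all of them fall in follow-up. This case is realistic, because the first dose is given at the baseline visit (Protocol section 6.1).

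**Could time of day rescue the rule?** Protocol section 8.3 requires an onset date for each AE and does not list an onset time. Protocol section 6.3.2 asks for the date and time of the last dose when a patient leaves the study, but Table 6 compares dates only. The general rule in SAP Table 3 on using times concerns the calculation of intervals, not the assignment of a period. Nothing else in either document overrides Table 6.

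**Is the sign a reading fault?** This is unlikely. The same symbol appears, with its expected meaning, in the TEAE column of Table 6 and in Table 7.

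**The case against.** The strongest case on the other side is that little depends on the split. The safety endpoint is TEAEs throughout the study (Protocol section 7.1.4; SAP section 3.2.4). The overview table and the severity tables have no period split, and each by-period table also has an overall column. ADR status follows the investigator's causality grade, and events are listed by patient. No between-arm test of AEs is planned. All of this stands, and it limits the point to the labelling of period.

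Five stronger readings are tempting and should not be drawn:

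- A reader might infer that about 10 of 100 patients are affected, from the planned 10% allowance. That figure covers dropouts or patients not evaluable (Protocol sections 4.4 and 9.1; SAP section 5). Protocol section 6.3.2 separates stopping treatment from leaving the study, so 10% does not bound the number who stop IMP in either direction. An affected patient must also have an event that starts exactly on the last dosing date; an event that starts earlier and leads to stopping later stays in the treatment period.
- A reader might infer that the rule favours cenegermin, or whichever arm is less well tolerated. The rule is identical in both arms, and the documents give no difference between arms in same-day stops.
- A reader might infer that a patient dosed only on Day 1 can have no on-treatment TEAE at all. SAP section 11.1 also counts pre-dose events that worsen. These start before the last dose, so the statement must be limited to new-onset events.
- A reader might cite the phase II account in Protocol section 2.2, that "Adverse reactions were mild and transient, and occurred only during the 4-weeks treatment period", as support. It concerns another study, and nothing shows that this rule was used there.
- A reader might take the assignment of undated events to the treatment period as proof that the rule for dated events is wrong. It is a cautious default for unknown dates. It does show that the same reaction is labelled treatment if poorly dated and follow-up if precisely dated, but the argument rests on sections 4.2 and 12.1.

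**Conclusion.** The rule is wrong as written; it is not merely short of detail. In patients who discontinue treatment, a new-onset TEAE with a known start on the last dosing day is tabulated under follow-up, although the SAP itself counts that day as exposure. This includes an event that causes the stop.

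The error is exactly one day per patient who stops early. It reaches only the on-treatment/follow-up columns of the six by-period summaries. The number of events involved cannot be derived from the documents, and no direction of bias between arms can be claimed. The conclusion assumes that the program follows Table 6 literally and compares dates without times.

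**What to change.** In the treatment-discontinuation branch of SAP Table 6, assign follow-up only if the AE start date is later (>) than the date of last IMP intake, and assign treatment otherwise. Treatment-period days then equal the Table 3 exposure days for these patients (10 and 10 in the example), and the case of dosing on Day 1 only resolves.

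The cost is one symbol in the SAP and the matching line of the program. No new data are needed and no clinical rule changes. The downside is that on-treatment counts may be slightly higher, and an event that began that day before the last drop would also count as on treatment.

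The adjacent branch, for patients who do not discontinue treatment, uses a Day 21 visit that is absent from the visit schedule in SAP section 4.4. That is a separate error, but it sits in the same table cell. Both branches are best corrected in one edit, with the boundary convention stated explicitly for each.
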